The study participants will be the junior and senior anaesthetic registrars from the Fiona Stanley & Fremantle Hospital Group Department of Anaesthesia & Pain Medicine. An email will be sent by [name] containing information regarding the study and a request for participation.

Participant inclusion criteria.

All the registrars in the Fiona Stanley & Fremantle Hospital Group Department of Anaesthesia & Pain Medicine as of 3rd August 2020.

Participant exclusion criteria.

Unwilling to participate or sign consent.

Not completing the chest drain training.

Adverse reaction to virtual reality hardware.

Previous use of the VR chest drain scenario if allocated to the control group.

Participant withdrawal criteria

If unable to use the virtual reality training program due to motion sickness, nausea or headache. The facilitators will attempt to improve the comfort of the headset. If the participant still cannot use the headset due to discomfort they will be removed from the study.

Bias

The participants will be allocated to groups by computer-generated randomisation. The assessors of the two groups will be blinded to the training method that all the participants received.

Blinding and Randomisation

Due to the varying skills/capabilities of the junior and senior registrars, the two groups will be randomised separately to ensure an equal balance between the control and experiment groups.

The researchers will have a separate list of participants that will contain the information regarding which training method each participant received. This will be correlated against the score sheets from the blinded assessors.

Method

The traditional education group will use the teaching material from the Emergency Trauma Management (ETM) course manual. This course is accredited as part of the professional development program by the Australian College of Rural and Remote Medicine. The VR education group will use the novel VR training software. Assessment of the two groups will be performed on a SimMan 3g mannikin with a chest drain module inserted. The assessment tool used is a validated checklist for chest drain insertion proficiency.

Project Duration/Schedule

The expected duration of data collection is six months. Data analysis is expected to take a further 6 months to complete. This includes the writing of a research manuscript for publication.

Project Termination

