Once all participants have completed their allocated training program and have been subsequently assessed by a blinded assessor the data collection process will end.

5 Treatment of Participants

Description and justification for treatments, interventions or methods to be utilised

The hypothesis that the VRE may prove to be a more effective training method is of potential benefit to all the study participants and patients, especially as this technology becomes more widely incorporated into medical training. The *"Traditionally trained"* group will not be disadvantaged as this is currently the accepted standard of training. Furthermore, access to the VR training software will be made freely available to all participants once their blinded assessment has been completed.

Permitted medications/treatments

There is no medication or treatment in this study.

Monitoring of participant compliance

Onsite facilitators will be present to conduct the virtual reality training session. Facilitators will further ensure that the traditional group reads the notes provided and watches the instructional video.

6 Assessment of Efficacy

Outcomes

Raw scores on the validated chest drain insertion competency checklist

Any deviation from the validated checklist

Time taken for task completion

Matched confidence scores using Likert data from a pre- and post-intervention survey.

Efficacy assessment

The TACTIC validated checklist for chest drain insertion competency will be used (10). The assessors will determine the number of deviations from the checklist and record the time taken to complete the procedure. Confidence levels will be assessed via matched Likert data.

7 Assessment of Safety

Risks and Benefits

Potential risks to the participants include motion sickness, nausea and headaches from the virtual reality training programme. Facilitators will attempt to improve comfort and ensure correct use of the virtual reality headsets in order to limit these effects. Infection risk and cross contamination will be managed by the use of a UVC irradiation device.

Emergent chest drain insertion is a potentially life-saving procedure and the benefits for potentially improving knowledge and skill of chest drain insertion is enormous.

Safety

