Facilitators will be present and monitor for any ill effects developing as a result of the training intervention. Infection control will be provided via UVC irradiation device, used on the virtual reality headset. The controllers will be wiped down with disinfectant wipes between uses.

Adverse events reporting

Any adverse events will be reported via the research team.

- Minor event: follow up with candidate
- More serious event: Regular follow up until resolved/ referral to care provider as determined by independent assessment.

Follow-up of Adverse Events

Any adverse events will be followed up until resolution of any symptoms.

8 Data Management, Statistical Analysis and Record Keeping

Statistics and Interim Analysis

Wilcoxon signed-rank test will be employed to assess any differences that may exist between the two groups. Likert-type questions will be used to obtain self-reported confidence data pre- and post-educational sessions. The median results of the Likert-type questions will be shown to describe central tendency.

Sample Size

The pilot project will use a convenience sample of Anaesthesia registrars at FSFHG. Currently there are 51 registrars. All registrars will be approached to participate. The study is a proof of concept study. Due to the fact that virtual reality software has only recently been developed, there is to the best of our knowledge no other published data to refer to. If a difference is noted between the study groups, a power analysis will be conducted to calculate the sample size necessary in a follow up study, to confirm differences that may exist.

Study Power and Significance

A validated checklist will be used to assess each candidate's placement of a chest drain. This checklist has 20 steps, graded out of 40 points, that must be completed in order for the chest drain placement to be deemed safe & successful. The mean score of the two study groups will be compared. A difference in the mean score p value of 0,05 will be deemed significant.

A power analysis will be conducted for a subsequent study, based on the results of this pilot trial.

As there is no data for VR teaching in terms of medical procedures in anaesthesia this study will provide a baseline comparison to traditional teaching. Certainly, an increase of 20% in the mean score would be seen as significant.

Statistical plan deviations

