There is no anticipated deviation from the scoring system used to assess the placement of the chest drain. Incomplete scoring systems will not be included in the final analysis but may be used to make trends in comparisons between the two groups. Should any unanticipated protocol deviation occur this will be reported to the hospital ethics committee and a decision to proceed further will be made by the investigators.

Selection of participants for analyses

Participant selection will be via a convenience sampling of Anaesthesia Registrars from the Department of Anaesthesia and Pain Medicine at FSFHG. All consenting and participating registrars will be included in the final analysis of the two teaching methods employed in the study.

Data Management

All of the participate data will be anonymised and deidentified. The data will be stored on the chief investigator's password protected work computer. The data will only be accessible by the research team. The computer is locked in a cupboard in the anaesthetic department, which is only accessible by staff access security badges. Access to this data will be further blocked by passwords to specific folders minimizing access. No personal data will be shared with any 3rd party sponsors or external teams. Data including electronic, hardcopy and consents will be stored for a period of 7 years from the period of publication and will be made available should a written request be made by the ethics committee or hospital board. The data, hardcopies and consents will be destroyed after 7 years.

Procedure for accounting for missing, unused, and spurious (false) data.

All collected data will be analysed by each member of the investigating team. Incomplete data will not be included in the final analysis. Incomplete data may be used to analyse trends in the data from which no final conclusions will be drawn. Incorrectly completed checklists will not be utilised for final analysis.

9 Monitoring / Audit

Monitoring, Audit and Regulatory Inspections Statement

The project investigators/institutions will permit project-related monitoring, audits, and regulatory inspections, providing direct access to source data/documents. This may include, but not limited to, review by external sponsors, Human Research Ethics Committees and institutional governance review bodies.

Procedures for Monitoring and auditing

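### VR access opens after each participant's own assessment rather than the last one, leaving an unguarded risk that waiting controls are exposed, and the protocol handles an exposed control inconsistently

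*Protocol*

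**What the plan says.** - **Release of the software** (Protocol section 5, description and justification of interventions): "access to the VR training software will be made freely available to all participants once their blinded assessment has been completed".
- **End of data collection** (section 4, under the Project Termination heading): "Once all participants have completed their allocated training program and have been subsequently assessed by a blinded assessor the data collection process will end". The release of VR access is not tied to this point.
- **Time frame** (section 4, Project Duration/Schedule): "The expected duration of data collection is six months".
- **Population** (section 4, inclusion criteria): "All the registrars in the Fiona Stanley & Fremantle Hospital Group Department of Anaesthesia & Pain Medicine as of 3rd August 2020". Section 8, Sample Size, adds "Currently there are 51 registrars", and all of them are to be approached.
- **Prior VR use** (section 4, exclusion criteria): a participant is excluded for "Previous use of the VR chest drain scenario if allocated to the control group".
- **Analysis set** (section 8, Selection of participants for analyses): "All consenting and participating registrars will be included in the final analysis of the two teaching methods employed in the study".
- **Supervision** (section 5, Monitoring of participant compliance): "Onsite facilitators will be present to conduct the virtual reality training session". Facilitators also oversee the reading and video session of the traditional group. Nothing is said about supervising VR use after a participant's assessment.

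**The concern.** The protocol regards VR use by a control as serious enough to exclude that person. Yet its release rule allows the software to circulate among that person's colleagues before data collection is over. Once the first participants have been assessed, nothing in the text prevents an assessed registrar from showing or lending the scenario to a control who is still waiting.

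If that happens, neither route open to the investigators is clean:

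- **Exposed control kept.** Part of the control arm has had some of the VR training, so the observed difference shrinks. Section 8 plans to size a follow-up study from this pilot, so a diluted estimate would carry forward.
- **Exposed control dropped.** The exclusion depends on allocation, so it acts after randomisation and in one arm only. Registrars who seek extra practice are unlikely to be a random subset of their arm, and removing them can shift the control mean.

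The protocol does not settle which route applies, because the section 4 exclusion and the section 8 analysis set give different answers. An analysis plan could choose between them, but could not undo the exposure.

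**Working it through.** **1. The passages side by side**

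| Question | What the protocol gives | What follows |
|---|---|---|
| When does access open? | After the participant's own assessment (section 5) | No hold until the last assessment |
| Can an unassessed control use the software under the rule? | No | Exposure needs sharing by an assessed colleague |
| Are the arms separated? | One department (section 4) | Both arms are colleagues |
| Are assessments spread out? | Six months expected; no schedule given (section 4) | Likely, but inferred |
| What happens to an exposed control? | Excluded (section 4); analysed if consenting and participating (section 8) | Unresolved |
| Does the prior-use exclusion apply to the VR arm? | No | One-sided and dependent on allocation |

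**2. What an exposure would do**

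The protocol makes no power claim, so there is no stated figure to reproduce. The arithmetic below is illustrative.

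Inputs from the protocol: 51 registrars, significance level 0.05, a 40-point checklist, and a 20% increase in mean score as the difference of interest.

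Assumptions:
- all 51 take part, split 26 VR and 25 control, and the test is two-sided;
- the effect Δ is 4 to 8 points (20% of 40 is 8; 20% of an assumed control mean of 20 to 30 is 4 to 6);
- the SD is 5 to 8 points;
- a share c of 10% to 30% of controls is exposed;
- each exposed control gains the full VR effect, which is the worst case for dilution.

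Formulas (normal approximation for a difference in means):
- Power ≈ Φ(Δ / (SD × √(1/n₁ + 1/n₂)) − 1.96)
- Exposed controls kept: Δ becomes Δ × (1 − c), with 26 and 25 participants
- Exposed controls dropped: Δ is unchanged and control n becomes 25 × (1 − c)

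With Δ = 5 and SD = 6, the standard error is 6 × √(1/25 + 1/26) = 1.681. With no exposure, 5 / 1.681 = 2.975 and Φ(2.975 − 1.96) = 84.5%.

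| Exposed | Kept: difference | Kept: power | Dropped: control n | Dropped: power |
|---|---|---|---|---|
| 0% | 5.0 | 84.5% | 25 | 84.5% |
| 10% | 4.5 | 76.3% | 22.5 | 82.5% |
| 20% | 4.0 | 66.3% | 20 | 80.0% |
| 30% | 3.5 | 54.9% | 17.5 | 76.9% |

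Over the whole grid of Δ and SD, 20% exposure costs from under 1 to about 19 percentage points of power if exposed controls are kept, and at most about 5 if they are dropped.

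The exact noncentral-t calculation runs slightly lower but shows the same pattern. For an assumed effect of 0.80 SD it gives 79.9% with no exposure; 71.2%, 61.0% and 50.0% at 10%, 20% and 30% exposure kept; and 74.9% with five controls dropped (26 against 20).

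**3. Selection when exposed controls are dropped**

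Suppose the dropped share c would have scored g points above those retained. The full control mean equals the retained mean plus c × g, so dropping them lowers the control mean by c × g. With g assumed at 2 to 4 points and c at 10% to 30%, the shift runs from 0.1 × 2 = 0.2 to 0.3 × 4 = 1.2 points, in favour of VR. If those dropped were weaker, the sign would reverse.

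**The case against.** The own-assessment condition is itself a safeguard: no control gains access under the protocol before being assessed. A reader might infer that contamination is certain, or that excluding exposed controls is the only protection. The text supports neither. Exposure needs informal sharing. The scenario also needs a head-mounted display, and the budget mentions a single VR-ready laptop, which may limit casual use. Staggered assessment is inferred from an expected duration, since no schedule or interval between training and assessment is given. All of this stands, and it makes the point a risk of unknown probability. It does not remove the risk, because use after assessment is not described as supervised and a hold until the end would cost little.

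The section 4 exclusion may also cover VR use before the study, and delaying access would not repair its dependence on allocation. That is right, and the fix treats it separately.

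Losses are not confined to controls: section 4 also removes participants for adverse reactions to the hardware or headset discomfort. The net direction of selection over both arms is therefore unknown. The argument in step 3 concerns this one rule only.

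A reader might infer that dilution would count as success, because the stated hypothesis is that VR is at least as effective. The documents do not support that reading. The null hypothesis is no difference, section 8 tests for a difference, and no equivalence margin or decision rule turns a null result into a positive finding.

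Finally, this is a proof-of-concept convenience sample with no power claim, and the larger power losses arise only if exposed controls are kept. Both statements are correct, so the figures serve as illustration and not as an estimate.

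**Conclusion.** The point holds as an unguarded risk joined to an internal inconsistency. Two things rest on the text. VR access is released person by person (the natural reading of the sentence) with no hold until the last assessment, in a single department. And an exposed control is excluded by a one-arm, allocation-dependent rule that does not fit the stated analysis set.

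That controls will still be waiting when colleagues gain access is a reasonable inference from the six-month window, but it is not stated. That any control will be exposed is not shown.

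The size cannot be derived. Under the assumptions above, 20% exposure would cost up to about 19 points of power if exposed controls are kept. If they are dropped, the cost is up to about 5 points plus a selection bias of unknown size and direction. The change is worth making because it is cheap and removes an avoidable source of bias.

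**What to change.** 1. In section 5, and in the participant information if it repeats the promise, open VR access to all participants only after the last participant has been assessed, which is the Project Termination point in section 4.
2. Ask about previous use of the VR scenario before randomisation, and apply any prior-use exclusion then, regardless of arm.
3. Ask about VR use outside the assigned training again at assessment, keeping the answer from the blinded assessors. Analyse anyone exposed after randomisation in the assigned arm, and report the number exposed. Some dilution is accepted in return for keeping the randomised comparison.
4. Reword the section 4 exclusion and the section 8 analysis set so that they agree.

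The cost is a few sentences of protocol text and one survey question. Participants assessed early wait for access, at most for the rest of the data-collection window. Section 5 already describes the traditional teaching as the accepted standard, so controls still receive that in the meantime.

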There are a number of advantages in the use of VRE and these include; repeatability, portability, selfdirected learning, data collection, and cost (8). Taekman et al attribute further human elements such as, instant feedback, rewards, competition, scalability, standardisation and convenience (9).

Virtual Reality Education provides an opportunity to deliberately practise rare, potentially lifesaving procedures and scenarios in a risk-free environment. These advantages make VRE an attractive educational tool, provided that the virtual reality education program is at least as effective or superior to the traditional education method. This remains the motivation behind this pilot study.

3 **Project Aims / Objectives / Hypotheses**

Primary objectives: Compare the effectiveness of VRE training with traditional education methods for the placement of a chest drain by anaesthesia registrars. Effectiveness of education will be assessed by proficiency of chest drain insertion, non-deviation from standardised chest drain checklist and the time taken to complete the task of chest drain insertion.

Secondary Objectives: Assessment of registrar levels of confidence regarding chest drain insertion pre- and post-educational sessions.

Hypothesis: VRE training is as effective if not superior to a traditional teaching approach for the insertion of chest drains.

Null Hypothesis: There is no difference in chest drain insertions outcomes when instructed by either a traditional or VR training approach.

4 Project Design

Project Design

Pilot study

Pre-test survey assessing prior chest drain insertion training; number of chest drain insertions performed in patients; current confidence level related to chest drain insertion ability.

Subjects randomly assigned to one of two groups

Traditional teaching method. Text and instructional video Virtual reality training method

All study participants will be assessed by two anaesthetic consultants blinded to group allocation using a validated checklist for chest drain competency. Chest drain insertion success with be assessed using scores from assessment tool, number of deviations from the checklist, time to task completion and self-reported chest drain insertion confidence levels.

Source and Selection of Participants

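### Time to completion has no value for a registrar who does not finish, and the incomplete-data rule, read plainly, drops that registrar from the time comparison

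*Protocol*

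**What the plan says.** Section 3 of the protocol (primary objectives) names three measures of effectiveness: proficiency, non-deviation from the checklist, and "the time taken to complete the task of chest drain insertion". Section 6 lists the outcome as "Time taken for task completion" and has the assessors "record the time taken to complete the procedure". No maximum attempt time, censoring rule or value for an unfinished attempt is given.

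Section 8 handles missing values in three places:

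- Procedure for accounting for missing, unused and spurious data: "Incomplete data will not be included in the final analysis". What is left out has a limited role: "Incomplete data may be used to analyse trends in the data from which no final conclusions will be drawn".
- Statistical plan deviations, on the checklist: "Incomplete scoring systems will not be included in the final analysis".
- Selection of participants for analyses: "All consenting and participating registrars will be included in the final analysis of the two teaching methods employed in the study".

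**The concern.** A completion time exists only if the procedure is completed. A registrar who stops has no time, and an absent time is incomplete data in the ordinary sense of the words. Under the stated rule that registrar leaves the time comparison. Completing the task is itself a possible result of the training, so comparing times among completers conditions on something that happens after randomisation. The protection that randomisation gives is then lost for one part of the primary objective.

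This differs from the exclusion of incomplete checklists. An unfinished attempt can have a fully scored checklist, with missed steps marked down, and still have no time. Repairing the checklist rule alone would leave the time comparison as it is.

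At stake is a time result that understates a real difference in speed or, in less likely circumstances, credits the arm in which more registrars failed. The protocol intends to size a follow-up study from these pilot results, so a distorted time result could carry forward.

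**Working it through.** **Reading the text.** The protocol has no time, failure rate or power figure to reproduce. Three statements stand side by side: time is defined by completion (sections 3 and 6); incomplete data are out of the final analysis (section 8); all consenting and participating registrars are in it (section 8). For a registrar with a scored checklist and no time, the last two cannot both be followed for the time outcome, and nothing says which prevails.

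**Inputs.** From the protocol: 51 registrars, taken as 26 v 25, and a 0.05 threshold (stated for the mean score; taken here as two-sided). Assumed: log-normal times with median 300 s and log-SD 0.4, and the failure rates below. The test is an unpaired Mann-Whitney comparison.

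**Case 1: equal underlying speed, failure 5% in arm A and 20% in arm B.** The mean time of all attempts is 300 × exp(0.4²/2) = 325 s in both arms. If failures are exactly the slowest attempts (correlation 1), the mean among the fraction p who complete is 325 × Φ(z_p − 0.4)/p:

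- Arm A: p = 0.95, z = 1.645, so 325 × 0.893/0.95 = 306 s.
- Arm B: p = 0.80, z = 0.842, so 325 × 0.671/0.80 = 272 s.

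Arm B looks about 33 s faster (before rounding) although speed is equal. Simulation with weaker links between slowness and failure gives:

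| Slowness-failure correlation | Apparent advantage of arm B | Arm B significantly faster, completers only |
|---|---|---|
| 0 | about 1 s or less | about 2% |
| 0.3 | 9 s | about 4% |
| 0.5 | 17 s | about 6% |
| 1 | 33 s | about 13% to 14% |

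Chance alone gives 2.5%. With non-completers ranked worst, arm B is significantly better in at most 1.6% of trials (0.2%, 0.7% and 1.6% at correlation 0, 0.5 and 1). These last figures come from a run with 25 v 26 registrars and coefficient of variation 0.4. In that run, more extreme failure of 10% v 40% gave 2.1%, 8.8% and 40.1% for completers only at the same correlations. Equal failure of 10% in both arms gave no distortion.

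**Case 2: arm B truly 40% slower, one common time limit.** The median in arm B is 1.4 × 300 = 420 s, and the true difference in means is 0.4 × 325 = 130 s.

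- Limit 600 s: failures are 1 − Φ(ln(600/300)/0.4) = 1 − Φ(1.73) = 4% and 1 − Φ(ln(600/420)/0.4) = 1 − Φ(0.89) = 19%. The completers' difference shrinks to about 77 s. Power is about 81% with worst rank and about 60% among completers.
- Limit 480 s: failures are 1 − Φ(1.18) = 12% and 1 − Φ(0.33) = 37%. Power is about 80% with worst rank and 42% among completers.

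No simulated trial at either limit gave a significant result in favour of the slower arm. Case 2 shows loss of a real difference, not reversal.

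**The case against.** The strongest reply is that the protocol never mentions a registrar stopping or giving up and sets no time limit. Without a limit, slow attempts finish and are timed, and nothing in the text ties abandonment to slowness. The remark in section 8 that the steps must be completed for a safe and successful placement concerns the checklist; an attempt with missed steps can still end and be timed. The incomplete-data sentence stands next to one on incorrectly completed checklists and may have been meant for faulty forms. Handling of non-completers is often left to a statistical analysis plan. The study is a proof-of-concept pilot whose stated threshold concerns the mean checklist score, where a failed attempt can still show.

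Most of this stands as a limit on size and likelihood. It does not remove the point. The protocol is not merely silent: it states an exclusion that, as worded, covers an absent time, and it states an inclusion that contradicts it. An analysis plan that followed the exclusion would inherit the problem.

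A reader might infer that the least able registrars will leave the time analysis, more of them from the worse-taught arm, and that the time result will therefore point the wrong way. The documents do not support that. Whether anyone fails, whether failure differs by arm and whether it goes with slowness are all unknown. Equal speed with unequal failure confined to the slowest attempts also needs a different cut-off in each arm, so correlation 1 in case 1 is an upper bound.

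**Conclusion.** The point holds in conditional form. Time to completion is undefined for a non-completer, and the section 8 exclusion, read plainly, takes that registrar out of the time comparison, in conflict with the statement that all participating registrars are analysed. Bias towards the arm that fails more needs three things: some failures, a different failure rate in each arm, and a link between failing and being slow. When they hold, the usual consequence is a hidden or shrunken difference. A false advantage becomes frequent only if the link is strong.

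The rates and times are assumptions, so the actual size cannot be stated. With no failures, equal failure, or failure unrelated to speed, the time comparison is not distorted, although any failures would still go uncounted in it. The change is worth making because it is cheap and needs to be settled before the first assessment. The test named in section 8 ("Wilcoxon signed-rank test will be employed to assess any differences that may exist between the two groups") is a paired test for two independent groups; that is a separate matter on which this conclusion does not depend.

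**What to change.** 1. In section 8, reconcile the two statements: say that the incomplete-data exclusion does not apply to a time that is absent because the attempt was not completed.
2. Keep every assessed registrar in the time analysis. Give non-completers the worst rank in an unpaired rank test. Alternatively, censor them at one maximum assessment time, the same in both arms and set before the first assessment, and use a log-rank test.
3. Report the number not completing in each arm beside the time result.

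The cost is a few sentences in sections 6 and 8 and one tick-box on the score sheet, with no extra registrars, staff or sessions. The small downside is that time becomes a rank or time-to-event result that combines speed with completion, rather than a simple mean. For example, with equal speed, 5% v 20% failure and correlation 0, the worst-rank test finds the failing arm significantly worse in about 14% of trials purely because more of its registrars failed. That is why completion must be shown alongside.

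### The protocol assigns a paired test, the Wilcoxon signed-rank test, to the comparison of two independent randomised groups

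*Protocol*

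**What the plan says.** - **Test.** Section 8, Statistics and Interim Analysis: "Wilcoxon signed-rank test will be employed to assess any differences that may exist between the two groups". The protocol names no other test.
- **Design.** Section 4, Project Design: "Subjects randomly assigned to one of two groups". Section 4, Bias: "The participants will be allocated to groups by computer-generated randomisation".
- **Stratification.** Section 4, Blinding and Randomisation, on junior and senior registrars: "the two groups will be randomised separately to ensure an equal balance between the control and experiment groups".
- **Paired data.** Section 6, Outcomes: "Matched confidence scores using Likert data from a pre- and post-intervention survey". These are the only paired measurements in the plan. Section 8 mentions confidence in the sentence after the test and describes it by medians, with no test attached.
- **Score and threshold.** Section 8, Study Power and Significance: "This checklist has 20 steps, graded out of 40 points"; "The mean score of the two study groups will be compared"; "A difference in the mean score p value of 0,05 will be deemed significant".
- **Analysis set.** Section 8, Selection of participants for analyses, keeps every registrar who consents and takes part in the final comparison.

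**The concern.** The signed-rank test takes one difference per pair, ranks the absolute differences and sums the ranks by sign. A registrar in the VR group has no partner in the traditional group, so these differences do not exist until someone decides who is matched with whom. The protocol gives no rule for that. An analyst must either invent a pairing or depart from the stated test.

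If a pairing is invented, the p-value belongs partly to the pairing, and a different choice can move it across 0.05. Anyone left without a partner is dropped, contrary to the stated analysis set. The sentence is not limited to one outcome, so the same problem reaches checklist score, deviations and time to completion. A noted difference between the groups is also what triggers the sample size calculation for the follow-up study, so the verdict has a use beyond this pilot.

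**Working it through.** The protocol gives no power or sample size calculation for this study, so there is no figure to reproduce. The check has three steps.

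**1. Test against design.** The signed-rank test needs d_i = x_i − y_i for each pair i. Section 4 supplies two separate groups and two grade strata. A stratum says which registrars are comparable as a set; it does not say which VR registrar is matched to which control. Even pairing within grade would leave the choice open. Only the pre/post confidence scores supply a natural d_i, within a participant.

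**2. Participants dropped.** With arm sizes n1 and n2, at most min(n1, n2) pairs can be formed and |n1 − n2| people are left out. Section 8 gives 51 registrars to be approached, which is a ceiling and not an enrolment figure, and no numerical allocation ratio is stated. If all 51 took part, |n1 − n2| would be odd, so at least 1 would be dropped; a 23/28 split, for illustration, would drop 28 − 23 = 5. Unequal arms are plausible: section 4 removes participants who cannot tolerate the headset, which arises in the VR arm, and excludes controls who have used the VR scenario before.

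**3. Does the pairing matter?** For 25 v 26 there are 26!/(26 − 25)! = 26!, about 4 × 10^26, possible pairings. The effect was simulated with scores rounded and capped at 40. *Arm sizes, means, SDs and differences are assumptions.* The protocol gives none of them, only a remark that a 20% rise in mean score would matter (6 points on a mean of 30; 5.6 on 28).

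Share of trials in which arbitrary pairings of the same data disagree at 0.05:

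| Control mean | Difference | SD | Two pairings | Six pairings |
|---|---|---|---|---|
| 30 | 4 | 5 | 9–12% | 23–25% |
| 30 | 6 | 5 | 2% | 4% |
| 28 | 5.6 | 5 | 2% | 6% |
| 28 | 5.6 | 6 | 7% | 17% |
| 30 | 6 | 8 | 11% | 26% |
| no true difference | 0 | – | 4% | 8–9% |

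Ranges within a row come from repeated runs. Over all the settings tried, the figures were about 1 to 12% for two pairings and 4 to 27% for six.

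Four single datasets show the mechanism. They were selected to be borderline (rank-sum p between 0.04 and 0.10; control mean 28, difference 3, SD 6), with 4,000 random pairings each:

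| Rank-sum p | Signed-rank p, lowest to highest | Pairings with p < 0.05 |
|---|---|---|
| 0.093 | 0.006 to 0.275 | 16% |
| 0.095 | 0.008 to 0.553 | 7% |
| 0.061 | 0.001 to 0.280 | 41% |
| 0.052 | 0.001 to 0.187 | 60% |

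The rank-sum test gives one p-value per dataset. Where the difference is clear, the pairing changes little: in three datasets with rank-sum p of 0.002, 0.005 and 0.006, all 2,000 random pairings gave p < 0.05.

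**One random pairing fixed in advance** (control mean 28, SD 6), rejection rate at 0.05:

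| True difference | Signed-rank | Rank-sum |
|---|---|---|
| 0 | 0.048 | 0.046 |
| 3 | 0.375 | 0.391 |
| 5.6 | 0.866 | 0.883 |

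**The case against.** *It is a slip for rank-sum, or was meant for confidence.* Either is possible. But the sentence ties the test to differences between the groups, and no independent-samples test appears anywhere in the protocol. A slip in the only named test still needs correcting.

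*The SAP can settle it.* An SAP may supply what a protocol omits. Here the protocol states a specific test that does not fit its design, and an SAP with a suitable test would contradict it.

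*It is a proof-of-concept study on a convenience sample.* This stands in part: it limits what rests on one p-value. The protocol nevertheless sets a 0.05 rule and uses a noted difference to launch the next calculation.

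Three stronger readings are tempting, and the documents do not support them:

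- *A reader might infer that the test inflates type I error.* It does not do so by itself. With one random pairing fixed in advance, the error rate is near nominal and the power loss is small. The exposure is a pairing that is undefined and could be chosen after the fact.
- *A reader might infer two incompatible analyses of one main outcome.* The mean-score sentence names no test, and section 3 puts proficiency, non-deviation and time together under the primary objectives. It is a secondary ambiguity: a rank test does not directly test a difference in means.
- *A reader might take a 25/26 split, and so the loss of one participant, as fact.* The 51 are those to be approached, and uptake is unknown.

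**Conclusion.** Wrong as written. The test named for the between-group comparison is a paired test, the design has no pairs across arms, and no suitable test is named elsewhere. This conclusion follows from the text alone and needs none of the simulation inputs.

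The size does depend on assumptions. Disagreement between arbitrary pairings is lowest when the true difference is large relative to the SD and highest when power is middling; no single percentage should be quoted for this trial. The practical harm is a verdict that cannot be reproduced from the protocol, together with the loss of unpaired participants when the arms are unequal.

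**What to change.** Replace the test sentence in section 8, Statistics and Interim Analysis, with:

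> Between-group differences in checklist score, number of deviations and time to completion will be tested with the two-sided Wilcoxon rank-sum (Mann-Whitney) test for independent groups, stratified by registrar grade (van Elteren). The Wilcoxon signed-rank test will be used only for within-participant pre/post change in confidence.

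In Study Power and Significance, reword the mean-score and p-value sentences so that the 0.05 threshold applies to this rank-sum test, and report group means descriptively.

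Stratifying by grade is optional. It reflects the separate randomisation of juniors and seniors and costs nothing, but it is not needed to correct the error.

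Cost: one or two sentences, and no extra data or participants. No sample size changes, because none was calculated.
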